APPLICATION FORM FOR THE RESEARCH PROTOCOL

Date: 15/07/2023

Número del estudio: REST-ECL-2023-08

Versión del protocolo: 2.0.

Fecha de la versión: 10/10/2023

Fecha de presentación: 15/07/2023

Investigador/a Principal: [name]

Investigador/a Secundario/a: [name], [name], [name]

Tutor/a / Monitor/a: [name]

Departamento: Odontología Restauradora y estética

Línea de investigación: Investigación básica y aplicada en odontología

Título de la investigación: "Clinical and anatomical factors influencing accuracy in fully guided implant placement"

1. Introduction.

Digital technologies have been widely used in current implant dentistry practice improving clinical outcomes. Computer-guided surgery (CGS) has been introduced to transfer the planned implant position from specific planning software to a surgical procedure. Therefore, implant placement using CSG provides better outcomes regarding the **3-Dimensional (3D)** implant position than free-hand implant placement, shorter surgical time, less discomfort to the patient, and allows prosthetically driven implant placement.¹

Nowadays, static system surgery has been more often applied in clinical practice than dynamic systems. The literature has reported that there exist cumulative sums of errors throughout the guided implant surgery sequence, for example improper

guide positioning. Mucosal thickness and mobility can be a variable that might affect the final position of the guide; therefore, the outcome of the implant position can be influenced as well.^{2,3}

Studies regarding the accuracy of implant placement with CGS have reported that there can be a deviation between planned and placed implant position. A recent systematic review has demonstrated that the total mean deviation of 1.2 mm (1.04–1.44 mm) at the implant platform level and 1.4 mm (1.28–1.58 mm) at the implant apex level was found in the case of implant placement with CGS.³

Several reports revealed that some clinical factors such as the surgical technique, guide type, and implant position can affect the accuracy of the implant placement with CGS.^{3,4}

Moreover, the impact of the jawbone condition, such as bone quantity and quality in the implant placement site, affecting the accuracy of implant placement with CGS remains unclear.^{4,5}

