Putra et al.⁶ reports that with low bone density, the drilling trajectory might deviate toward the softer part of the bone after the second drilling procedure. Therefore, highest deviation was found in the cases that the bone density was less than 500 Hounsfield unit (HU).

Multiple bone condition predictors like bone density, bone width, and cortical bone thickness significantly influenced the accuracy in implant placement with CGS.

Some other factors like implant site, type of implant (immediate, early or delay), mucosal thickness, graft in the area, quantity of implants have been reported as a factor influencing the accuracy of the guided surgery.^{6,7}

The aim of this cohort prospective study is to assess the influence of clinical and anatomical factors on the accuracy of computer-guided surgery. The following factors will be taken into consideration for the analysis of the data: 1) Implant location (anterior or posterior); 2) Single or multiple implants; 3) Mucosal thickness; 4) Native or regenerated bone, 5) immediate or delay implant.

2. Objectives.

Overall objective.

The aim of this cohort prospective study is to assess the influence of clinical and anatomical factors on the accuracy of computer-guided implant surgery on immediate and delayed implant placement:

Specific objectives:

- 1) To assess the influence of implant location (anterior or posterior) on the accuracy of CGS
- 2) To assess the influence of time for implant placement (immediate or delay) on the accuracy of CGS.
- 3) To assess the influence of type of bone (native or regenerated bone)
- 4) To assess the influence of bone density on the accuracy of CGS.

Hypothesis.

- 1: H1 implant location (anterior or posterior) has an influence on the accuracy of CGS
- 2: H1 The time for implant placement (immediate or delay) has an influence on the accuracy of CGS.
- 3: H0 The mucosal thickness does not have an influence on accuracy of CGS.
- 4: H1 The bone density has an influence on the accuracy of CGS.

Material and methods.

The study will be performed at a private practice (Blasi Dental Clinic) which is under the tutelage of the Universitat Internacional de Catalunya (UIC) CElm.

Moreover, the present study will be registered in clinicaltrials.gov.

For the sample size calculation, we use as reference Putra's¹⁴ article where it is reported correlations between different deflection parameters and bone density. These are weak-moderate magnitude correlations (0.3<r<0.5).

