The sample size was calculated for 3 levels of statistical power, a 95% confidence level with Pearson's linear correlation coefficient null test)

Degree of correlation Power reached

	70%	80%	90%
r=0.3 (weak)	67	84	112
r=0.5 (moderate)	23	29	37

To detect a weak magnitude correlation as significant, 84 patients will be needed for this study.

Inclusion criteria.

- Patients between 25 to 60 years old.
- Periodontally stable patients. Adequate oral hygiene with less than 15% Full Mouth Plaque Score (FMPS).
- Patients who need dental implant treatment without simultaneous regeneration.
- Ability to follow instructions and availability to attend for regular compliance during the entire study.
- With presence of partial edentulism (at least 6 remaining teeth distributed in the dental arch to support the guide).

Exclusion criteria:

- Active infections

- Untreated periodontal disease
- Heavy smokers (>10 cigarettes per day)
- Drug / Alcohol dependency
- Medical condition contraindicating implants dependency
- Patients under bisphosphonate therapy
- Limited mouth opening

All the information will be given to the patients before sign and obtain the informed consent form.

Clinical procedures.

After assessing the fulfillment of the inclusion criteria, pre-operative cone beam computed tomography (CBCT) (Newtom, Cefla S.C.) and intraoral digital impressions (Trios®, 3Shape Dental Systems, Denmark) will be obtained for each patient to achieve a digital wax-up and a presurgical plan for the exact position of the implants by a single calibrated operator (RP).

Every patient could have a maximum of four implants to be placed (one per quadrant), in those cases, there will be one guide per implant.

The digital imaging and communications in medicine (DICOM) files will be imported to a guided-surgery planning software (Codiagnostix, Dental wings) to perform an implant planning based on the digital wax up; in this step the assessment of the mucosal thickness will be performed using the STL and the DICOM files superimposed. The measurement will be taken from the crestal bone until the soft tissue surface (mm).

Furthermore, a surgical guide will be designed, and 3D printed (SprintRay Pro S; SprintRay Inc) with implant guide resin (SprintRay EU Surgical Guide Clear; SprintRay Inc) by RP for the surgical procedure, supported by the whole dental arch, and reinforced with one bar across the arch.

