Through guided surgery, previously planned and designed based on CBCT study and CAD/CAM scanning, placement of Conelog Progressive line implants

(Biohorizons Camlog, Iberia) will be performed in maxilla or mandibula in a one stage surgery by a 8 years' experience operator (GB).

Implant placement will be fully guided and a postoperative CBCT in ECO mode ($35\mu\text{Sv}$) will be taken after the implant placement to assess the final position.

Both CBCT will be aligned (pre-op scan and post-op scan) to make calculations by a single evaluator (AB) included the following (Fig. 1): (1) angle: angle deviation measured in degrees; (2) base: deviation at implant shoulder in millimeters; (3) tip: deviation at implant apex in millimeters; (4) 3D offset: global deviation in 3D directions in millimeters; (5) mesiodistal deviation in millimeters: (+) deviated to the distal direction and (-) deviated to the mesial direction; (6) buccolingual deviation in millimeters: direction: (+) deviated to lingual direction and (-) deviated to buccal direction; and (7) apicocoronal deviation in millimeters: direction: (+) deviated in the apical direction. and (-) deviated in the coronal direction.

[figure not shown]

Figure 1. Parameters to evaluate de position of the implant. ¹⁴

Clinical and study schedule

The estimated appointments for all patients:

- Screening visit: Selection, recruitment of patients, and signing of informed consent.
- First visit: Data collection (intraoral scanning and CBCT acquiring).
- Second visit: Implant placement and post-operative CBCT.

Ethics

This protocol follows the ethical principles regarding human experimentation recommended by the World Medical Association in the Declaration of Helsinki.

After fulfilling the inclusion criteria, all patients will receive a full informed consent.

After evaluation and clarification of possible concerns, the patient will return the signed consent as an agreement of participation.

Statistical analysis.

A descriptive analysis will perform by analyzing the mean, standard deviation, minimum, maximum values, and median for each outcome. For a 95% confidence level and an estimated standard deviation, T-test and Pearson's linear correlation coefficient null test will be used to analyze the data.

Study limitations

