This clinical study presents some limitations to be taken into considerations. First, if the surgical guide could not fit properly, present movements or break during the procedures, Second, the need of taking two CBCT in one month can represent a topic to be aware. And finally, the data should permit the correct alignment for further analysis and evaluation and its quality must be enough to facilitate the data analysis.

Contingency plan.

Rewarding the mishap of the fitting of the guide, in those cases we will print two guides per case, to have a backup if the first guide breaks. If the guides are not fitting properly, the patient should be excluded from the study.

[figure not shown]
For this study we will use the ECO mode which only presents a minimum effective dose of 9 μ Sv (four times less radiation than a regular CBCT and almost the same radiation as an orthopantomography)

Moreover, if any of the data collected presents any error that could interfere in the data analysis, the patient will be excluded for the study.

Annexes

- a. Flow chart
- b. Patient data collection
- c. Timeline

a. Flow chart

b. Data collection

PATIENT DATA COLLECTION	
PATIENTS PRE-SURGICAL INFORMATION	
Patient number: _____	
Age: _____	
Sex: _____	
Medical conditions _____	
Allergies: _____	
Smoker: Yes _____ No _____ How many per day? _____	
Site of implant placement: _____	
Immediate implant? Yes _____ No _____	
Native bone? Yes _____ No _____	
Single or multiple implants? _____	
Mucosal Thickness (millimeters) _____	
Bone Density (Hounsfield units) _____	
Complications with the surgical guide? Yes _____ No _____	
Other complications _____	

c. Timeline of study

Glosario de términos.

- 1. Computer-guided surgery (CGS)**
- 2. Cone beam computed tomography (CBCT).**
- 3. 3-Dimensional (3D)**
- 4. Hounsfield unit (HU).**
- 5. Full Mouth Plaque Score (FMPS).**

Investigador Principal [name]

Fdo: [name]

IP or tutor signature

Supporting researcher:

--	--

2.

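### Apex (tip) deviation rises on average with implant length, which the plan neither fixes nor records, so an unadjusted tip difference between factor levels may partly reflect length

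*Combined protocol and SAP*

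**What the plan says.** The protocol's Clinical procedures section defines seven deviations between planned and placed position. Three matter here: "1) angle: angle deviation measured in degrees", "2) base: deviation at implant shoulder in millimeters" and "3) tip: deviation at implant apex in millimeters". No outcome is named as primary.

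On the implant itself, the same section gives only the product line ("placement of Conelog Progressive line implants"). Position is planned case by case; the software is used "to perform an implant planning based on the digital wax up". No length is fixed, restricted or matched.

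The Introduction lists the factors for analysis as "1) Implant location (anterior or posterior); 2) Single or multiple implants; 3) Mucosal thickness; 4) Native or regenerated bone, 5) immediate or delay implant", and the specific objectives add bone density. Length is not among them. The form in Annex b has fields for site, timing, bone type, single or multiple implants, mucosal thickness and "Bone Density (Hounsfield units"), but none for length. The Statistical analysis section plans descriptive statistics, t-tests and Pearson correlation, with no covariates.

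For context, the Introduction cites a systematic review with mean deviations of "1.2 mm (1.04–1.44 mm) at the implant platform level and 1.4 mm (1.28–1.58 mm) at the implant apex level".

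**The concern.** The apex lies one implant length away from the shoulder, so a given tilt moves it further on a longer implant. Shoulder deviation and angle carry no such dependence. The apex therefore mixes how accurately the implant was placed with how long it is.

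This matters because the study aims to attribute differences in accuracy to location, timing, bone type and density. Patients are not randomised to these factors, so nothing in the design balances length across their levels. If, say, anterior and posterior implants differ in mean length, the planned t-test on tip deviation could show a location difference when guide, drilling and seating were equally accurate. Without length in the dataset, the analysis could not tell the two explanations apart on that outcome.

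**Working it through.** **1. The plan's own figures.** Fisher's z for r = 0.3, 80% power and two-sided 5% gives ((1.960 + 0.842)/atanh 0.3)² + 3 = 84.93. With the bias correction r/(2(n − 1)) it gives 83.98, which rounds up to the stated 84. The sample size is sound on its own terms and this point does not change it. The cited platform and apex means differ by 1.4 − 1.2 = 0.2 mm.

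**2. Geometry.** For a rigid implant of length L:

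tip vector = shoulder vector + L × (placed axis − planned axis), where the axis difference has size 2 sin(θ/2) for angular error θ.

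Per mm of length this is 0.044, 0.061 and 0.087 mm at 2.5, 3.5 and 5 degrees.

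The terms add as vectors, so direction matters. With a 1.2 mm shoulder error and 3.5 degrees, the angular part is 9 × 0.0611 = 0.550 mm at 9 mm and 13 × 0.0611 = 0.794 mm at 13 mm:

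- perpendicular to the shoulder error: √(1.2² + 0.550²) = 1.32 v √(1.2² + 0.794²) = 1.44 mm
- same direction: 1.75 v 1.99 mm
- opposite direction: 0.65 v 0.41 mm, so the longer implant has the smaller value

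**3. Average effect.** Inputs to a simulation with identical accuracy in both groups:

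- mean 3D shoulder error 1.2 mm, random direction (size from the Introduction)
- Rayleigh-distributed tilt in a random direction, mean 2.5, 3.5 or 5 degrees (assumed; the documents give no angle)
- lengths 9, 10, 11 and 13 mm (assumed; the documents give none)
- 42 v 42 implants, from 84/2, one implant per patient and an equal split (assumed)

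Mean tip deviation at 9 and 13 mm is about 1.27 and 1.34 mm (2.5 degrees), 1.33 and 1.45 mm (3.5 degrees), and 1.45 and 1.67 mm (5 degrees). At 11 mm and 3.5 degrees it is 1.39 mm, close to the cited 1.4 mm, so the inputs are not out of line with the protocol's source.

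Rejection is that of a two-sided 5% t-test with d = difference/pooled SD, non-centrality d√(42/2) and 82 degrees of freedom.

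| Contrast | Mean difference, mm (2.5 / 3.5 / 5 degrees) | Rejection, % (2.5 / 3.5 / 5 degrees) |
|---|---|---|
| 9 v 13 mm | 0.069 / 0.124 / 0.223 | 8.7 / 15.8 / 31.8 |
| 9 v 11 mm | 0.032 / 0.058 / 0.106 | 5.8 / 7.4 / 11.5 |
| 10 v 11 mm | 0.017 / 0.030 / 0.055 | 5.2 / 5.6 / 6.6 |

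For identical shoulder and tilt errors, tip deviation is smaller at 13 mm than at 9 mm in 27%, 21% and 14% of draws at the three angles.

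**4. Sensitivity to shoulder error.** If mean shoulder error were 0.6 mm, half the cited figure, the 9 v 13 mm difference would be 0.08 to 0.30 mm over 2 to 5 degrees, with rejection towards the longer implants of 21 to 72%. The result depends on an input that the study itself will supply.

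**The case against.** **Imbalance is not documented.** The documents contain no length data and do not say how length is chosen. A reader might infer that the factor comparisons do compare lengths. The text supports only a risk, of unknown size. This stands.

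**The effect is an average.** A reader might infer that the same shoulder and angular error always give a larger tip value on a longer implant. Vector addition rules that out, as the 14 to 27% of reversed draws show. This stands.

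**The 4 mm contrast is extreme.** It needs every implant in one group to be 9 mm and every one in the other 13 mm. With a 1 to 2 mm difference, rejection at 3.5 degrees stays near nominal (5.6 to 7.4%). This stands, and is why the shorter contrasts are shown.

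**Length may be a mediator.** If location determines length and length moves the apex, the raw comparison is a legitimate total effect of location on apex position. A reader might infer that the raw tip result is uninterpretable or should be replaced; the objectives, which ask about influence on accuracy, do not settle that. This stands against replacing the raw comparison, but not against showing an adjusted one beside it.

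**Length-free outcomes are already planned.** A tip difference with no difference in angle or shoulder deviation would be a warning sign. That helps, but without length the explanation could not be tested.

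**The form may not be the whole dataset.** It is headed as pre-surgical and lists none of the seven outcomes, and the flow chart is not shown. Planned length should also be recoverable from the planning files. So the information is probably not lost, but no readable text plans to collect or use it.

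**Conclusion.** The point holds as a possible bias in one outcome. The geometric dependence is certain on average for any non-zero angular error. The absence of a stated length restriction, record or adjustment can be checked in the text. Whether length differs between factor levels is unknown.

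Under the stated assumptions, a complete 9 v 13 mm contrast gives a spurious 0.07 to 0.22 mm, comparable at its upper end with the 0.2 mm platform-to-apex gap in the protocol's own citation. Differences of 1 to 2 mm give about 0.02 to 0.11 mm. Rejection against a nominal 5% is about 9 to 32% in the first case and 5 to 12% in the others. Those figures rest on assumed lengths and angles and an equal split of 84 single implants.

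Angle, shoulder deviation and the sample size are unaffected. The protocol does not say at which point 3D offset and the three directional deviations are measured; any taken at the apex would share the problem. The documents do not support the conclusion that the planned tip results are wrong, only that they could not be fully interpreted without length.

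**What to change.** 1. Add planned implant length, taken from the planning file, to the Annex b form. This asks only for recording; it does not ask for any change in which implant is placed.
2. Tabulate length by level of each binary factor, and its correlation with bone density and mucosal thickness.
3. For tip deviation, report each factor comparison twice: raw as planned, and adjusted in a regression with length as covariate. If shoulder and tip vectors can be exported in one coordinate frame, deviation at a common depth d is an alternative: shoulder vector + (d/L) × (tip vector − shoulder vector), with d no greater than the shortest implant, to avoid extrapolating beyond an apex. The protocol does not show that these vectors are available, so the covariate model is the default.
4. State in advance that a tip difference will be attributed to surgical accuracy only if it persists after adjustment or also appears in angle or shoulder deviation.
5. State the measurement point for 3D offset and the directional deviations.

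The cost is one form field and one extra model per factor, with no added scan, visit or patient. The raw apex value remains as the total effect and for comparison with the literature. One limit remains: if length and a factor almost coincide, adjustment cannot separate them, and the table in step 2 will show this.

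### No magnitude step is stated for the three signed axis deviations (outcomes 5–7), so on the plain reading their means, t-tests and Pearson tests compare mean drift, not size of error

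*Combined protocol and SAP*

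**What the plan says.** The protocol's Clinical procedures section lists seven outcomes computed from the aligned scans. The first four (angle, base, tip, 3D offset) carry no sign; the fourth is "4) 3D offset: global deviation in 3D directions in millimeters". The last three carry opposite signs for opposite directions:

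- The first signed axis is given as "5) mesiodistal deviation in millimeters: (+) deviated to the distal direction and (-) deviated to the mesial direction".
- The second signed axis, lingual against buccal, follows the same pattern, with lingual positive.
- The third signed axis is given as "7) apicocoronal deviation in millimeters: direction: (+) deviated in the apical direction. and (-) deviated in the coronal direction".

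The Statistical analysis section has two relevant statements. On description: "A descriptive analysis will perform by analyzing the mean, standard deviation, minimum, maximum values, and median for each outcome". On inference: "T-test and Pearson's linear correlation coefficient null test will be used to analyze the data". It does not say which test goes with which outcome. Nowhere do the documents state an absolute value, a root mean square or any other magnitude step, or a separate analysis of direction.

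The overall aim and all four entries under Hypothesis concern accuracy, for example "4: H1 The bone density has an influence on the accuracy of CGS". No hypothesis names an axis, and no primary outcome is named.

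**The concern.** Accuracy is about how far the implant lies from its planned position. A signed mean is about which way it drifts on average. Two implants at +1 mm and −1 mm have a signed mean of (1 − 1)/2 = 0, the same as perfect placement, while their mean absolute error is (1 + 1)/2 = 1 mm.

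If the tests are run on the values as defined, two misreadings of an axis result are possible. A null result may be taken as no effect on accuracy when errors on that axis have grown. A significant result may be taken as worse accuracy when only the direction differs. Leaving the scale open also lets it be chosen after the results are seen.

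**Working it through.** **The plan's own figure.** The Material and methods section concludes: "To detect a weak magnitude correlation as significant, 84 patients will be needed for this study". With r = 0.3, two-sided 5% and 80% power, n = ((1.960 + 0.842)/atanh(0.3))² + 3 = (2.802/0.3095)² + 3 = 84.93. A variant with a t critical value and bias correction gives 84.07. The stated 84 reproduces to within one patient. The formula contains only r, alpha and power, so N does not change with the scale chosen for outcomes 5–7.

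**Inputs for the illustration.** The sign conventions and the tests come from the protocol. The documents give no SD, drift or group split for the axis deviations, so those are assumed: normal errors, base SD 0.5 mm, 42 against 42, one implant per patient (the protocol allows up to four). Tests are two-sided at 5%, using the Welch t-test for groups. Each case has 20,000 replicates, so simulation error is at most √(0.25/20,000) = 0.35 percentage points (standard error).

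**(a) All errors on one axis scaled k-fold in one group.** Group 1 is N(d, 0.5) and group 2 is N(kd, 0.5k). Percentage of replicates rejecting, signed / absolute:

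| Drift d (mm) | k = 1.5 | k = 2 |
|---|---|---|
| 0 | 5 / 66 | 5 / 98 |
| 0.2 | 11 / 67 | 21 / 98 |
| 0.3 | 19 / 68 | 40 / 98 |
| 0.5 | 43 / 74 | 81 / 99 |
| 0.7 | 70 / 84 | 98 / 100 |

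The signed test sees only the difference in means, (k − 1)d. At d = 0 that is zero, so it rejects at its null rate. At d = 0.5 and k = 2 it is 0.5 mm, against a standard error of 0.5 × √((1 + 4)/42) = 0.173 mm. That is 2.9 standard errors, hence the 81%. The loss therefore shrinks as drift grows.

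For smaller rises with zero drift, the absolute test rejects 19% (k = 1.2) and 33% (k = 1.3), against 5% on the signed scale.

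**(b) Only the spread rises, with the same 0.5 mm drift in both groups.** Signed / absolute: 5 / 27 at 1.5-fold and 5 / 74 at 2-fold. The absolute test weakens here too, which is why the signed SD should also be reported.

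**(c) Equal error size, opposite drift (−0.2 against +0.2 mm).** The signed test has noncentrality 0.4/(SD × √(2/42)), which is 3.67, 2.44 or 1.83 at SD 0.5, 0.75 or 1.0 mm. The rejection rates are about 95%, 68% and 44% (simulation agrees to within a point). The absolute test rejects 5%, its null rate.

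**(d) Continuous factor, Pearson, n = 84.** Errors change 2-fold linearly across the factor's range. With drift of 0, 0.5 or 1 SD, signed / absolute rejections are about 5 / 62, 14 / 62 and 40 / 70.

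**(e) How far outcome 4 covers the gap.** Take 3D offset as the length of the three-axis vector (an assumption) with zero drift. A t-test on it detects a 1.5-fold or 2-fold rise on all three axes 99% or 100% of the time, but 40% or 88% when only one axis worsens. The absolute test on that axis gives 66% or 98%.

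**(f) Skew of absolute values.** With no true difference, the absolute-value Welch test rejects 5% at 42/42, 5% at 28/56 and 6% at 14/70.

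**The case against.** The strongest reply is that signed recording is no error. The Introduction cites a directional mechanism, in which the drill path drifts into softer bone, so direction is of interest. Outcomes 1–4 can be read as size and outcomes 5–7 as direction, and the gap is then a missing label. Each signed value still contains its size, and the planned SD, minimum and maximum would show spread. The sentence on tests does not assign them to outcomes 5–7 at all. A conversion may be intended: the figure that defines the parameters is not available here, and no conclusion can be drawn from its absence.

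Much of this stands. Signed testing is the plain reading, not an explicit rule. Signed values should be kept. The signed test does respond to growth in error when drift is large, as the lower rows of (a) show. The assumed cases of 1.5- and 2-fold also favour the absolute scale, since at 1.2- to 1.3-fold it mostly misses the change too.

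What remains is that the plan frames everything as accuracy, labels nothing as direction, and summarises each outcome by its mean. The SD and range are descriptive only and come with no test.

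A reader might infer that the study's accuracy conclusions as a whole are undermined. The documents do not support that: four unsigned outcomes remain, and every hypothesis can be answered through them. Nor do they support reading 84 as wrong on this account.

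**Conclusion.** The point holds as a minor one. The documents state no magnitude step for outcomes 5–7, and on the plain reading the axis-level tests compare mean signed drift. The possible harm is confined to three of seven outcomes and runs both ways: growth in error missed when drift is small or shared, and a difference in direction taken for a difference in accuracy.

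The simulated percentages illustrate the mechanism under assumed SDs, drifts and equal groups. They are not estimates of harm in this study. The cancellation itself follows from the sign convention and does not depend on those assumptions; its size does.

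**What to change.** In the Statistical analysis section, state that for outcomes 5–7 the accuracy descriptions, t-tests and Pearson tests use the absolute deviation. Report the signed mean with its 95% CI and the signed SD separately, labelled directional bias and spread, and say that they are not interpreted as accuracy.

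A rank-based check (Mann–Whitney, or Spearman for mucosal thickness and bone density) is optional, since (f) shows that the absolute-value test holds its error rate. If used, it should be labelled a sensitivity analysis, with the absolute-value test governing. It usually has less power (52% against 66% in the 1.5-fold, zero-drift case) and adds a second test for each axis and factor.

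The cost is a few sentences, a little extra analysis and a few more reported quantities. The absolute value comes from the same measurement, so no new data, visit or scan is needed, and N = 84 stays as it is. The wording should be fixed before the deviations are analysed.

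### Only one-factor tests are planned in an observational cohort: objective 4 (bone density) needs an adjusted analysis, and the plan should say whether the other effects are crude or adjusted

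*Combined protocol and SAP*

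**What the plan says.** The whole inferential plan is one sentence under Statistical analysis: after descriptive summaries, a t-test and Pearson's "linear correlation coefficient null test will be used to analyze the data". No section gives a regression, partial correlation, stratification, matching or covariate list.

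The questions are wider than that. The Introduction says "The following factors will be taken into consideration for the analysis of the data" and lists location, single or multiple implants, mucosal thickness, native or regenerated bone, and immediate or delayed placement. Specific objective 4 adds a sixth factor: "To assess the influence of bone density on the accuracy of CGS". The Hypothesis section is phrased in the same way, for example "The time for implant placement (immediate or delay) has an influence on the accuracy of CGS" and, as a null, "The mucosal thickness does not have an influence on accuracy of CGS". The study is a prospective cohort, so none of these factors is allocated.

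The Introduction also accepts that many factors matter at once: "Multiple bone condition predictors like bone density, bone width, and cortical bone thickness significantly influenced the accuracy in implant placement with CGS", and implant site and type, "mucosal thickness, graft in the area, quantity of implants have been reported as a factor influencing the accuracy of the guided surgery".

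The sample size rests on a single unadjusted correlation with density: "To detect a weak magnitude correlation as significant, 84 patients will be needed for this study". Study limitations covers guide fit, the two scans and data quality, but not confounding. The data collection form (Annex b) has a line for each of the six factors.

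**The concern.** A t-test or a Pearson test shows whether one factor is associated with deviation. If factors travel together, it cannot show which of them is responsible. The objectives speak of influence, and the background treats several of these factors as affecting accuracy, so a reader will take a significant result as evidence about that factor itself.

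Objective 4 is the clearest case. Location, timing and bone type could each be related both to density and to accuracy. If so, following the plan exactly could attribute location's effect to density, hide a real density effect, or inflate one. Nothing in the plan would show whether this had happened, and nothing warns the reader that the results are unadjusted.

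**Working it through.** **1. The plan's own figure.** Inputs from the sample-size text: r = 0.3, 95% confidence (two-sided 5% matches the table; one-sided does not), 80% power. Fisher z gives n = ((1.960 + 0.842)/atanh 0.3)² + 3 = (2.802/0.3095)² + 3 = 84.9, against 84 stated. Power at 84 is Φ(0.3095 × √81 − 1.960) = 79.6%. The stated number is right for one unadjusted correlation.

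**2. False signal for objective 4.** The documents give no overlap between factors and no location effect, so every input here except n = 84 is an assumption: one implant per patient, location split 50:50, density = gap × location + N(0,1), deviation = d × location + N(0,1), and no density effect. The correlation that location alone induces between density and deviation is

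r = (gap × d/4) / √[(1 + gap²/4)(1 + d²/4)].

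The rejection rate is approximately Φ(9·atanh r − 1.96) + Φ(−9·atanh r − 1.96). For d = 0.6:

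| Density gap (SD) | Induced r | Closed form | Simulated, unadjusted | Simulated, adjusted for location |
|---|---|---|---|---|
| 0.25 | 0.036 | 6.2% | 6.2% | about 5% |
| 0.5 | 0.070 | 9.6% | 9.5% | about 5% |
| 1.0 | 0.129 | 21.4% | 21.6% | about 5% |
| 1.5 | 0.172 | 34.7% | 35.7% | about 5% |

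Over the same gaps, the simulated range is 5.3% to 12.7% for d = 0.3 and 6.9% to 54.9% for d = 0.8. With a split of about 30:70 and d = 0.6 it is 5.8% to 28.0%. At a gap of zero the induced r is zero and the rate is the nominal 5%.

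**3. A real density effect, masked or exaggerated.** Assume a within-location r of −0.3 and a 0.6 SD location effect.
- Location acting against density: unadjusted power is 67.1%, 58.0%, 46.5% and 45.5% at the four gaps.
- Location acting in the same direction: about 86.0%, 92.2%, 98.6% and 99.8%.
- Adjusted for location: about 79.6% in either case.
- With no overlap, unadjusted power is already 76–77%, so about 3 points of the loss come from unexplained location variance rather than confounding.

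**4. What adjustment costs in power.** With k adjusters, power is Φ(atanh(partial r) × √(84 − 3 − k) − 1.96). For a partial r of 0.3 and k = 5 this is Φ(0.3095 × √76 − 1.96) = 77.0%. Now let R² be the share of density's variance that the adjusters explain, and e the share of outcome variance that they explain beyond density. Then

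partial r = 0.3√(1 − R²) / √(0.09(1 − R²) + 0.91 − e).

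| R² (assumed) | Power, e = 0 | Power, e = 0.10 |
|---|---|---|
| 0.059 | 74.5% | 79.2% |
| 0.20 | 67.8% | 72.6% |
| 0.36 | 58.3% | 63.2% |
| 0.50 | 48.5% | 53.0% |

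The first three R² values are those implied by density gaps of 0.5, 1.0 and 1.5 SD, from (gap²/4)/(1 + gap²/4). Overlap lowers power, and adjusters that explain deviation raise it.

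**The case against.** The strongest defence is that crude associations are the target. The sample size is built on a marginal correlation with density, so the crude reading is the only one that the documents quantify. For location, timing and bone type, a total effect, including whatever runs through density, is an equally natural question, and a t-test addresses it. This stands, and for that reason no error rate is claimed for those comparisons. It does not fully answer the point, because the plan never declares the crude reading and the limitations never warn of confounding.

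A second defence is that the size of the harm is assumed. The documents list the factors as separate influences and do not say that they are linked. This also stands: the grid above runs from no practical harm to serious harm. It limits what can be claimed, but does not remove the gap in the analysis.

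A reader might go further and infer that the planned tests for all four objectives are invalid, that confounding has been shown, or that 84 patients are too few. The documents support none of these. Choosing among the seven deviation measures and the layout of the data form are separate matters that this point does not need.

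**Conclusion.** The omission is certain from the text: one-factor tests only, no adjusted analysis, no statement that effects are crude, and no mention of confounding. The consequence is shown for objective 4 alone and depends on overlap that the documents do not give. Under the stated assumptions, a false density signal occurs at close to the nominal 5% when overlap is slight and in about a third of studies when the locations differ by 1.5 SD in density. A real density effect can be distorted in either direction. For objectives 1–3 and hypothesis 3, the defect is an undeclared estimand, not a demonstrated error. The point should be fixed before analysis, with medium confidence in how much it matters. The figure of 84 is correct for what it states.

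**What to change.** 1. Keep the planned t-tests and correlations, and label them as unadjusted associations.
2. For objective 4, prespecify a regression of deviation on density, adjusted for location, timing, bone type, mucosal thickness and single or multiple placement. Allow for implants in the same patient (for example with a patient random intercept), since Clinical procedures permits up to four per patient.
3. For objectives 1–3 and hypothesis 3, state whether the crude (total) or the mutually adjusted effect is intended, and report adjusted estimates as supporting.
4. Add residual confounding to Study limitations. Bone width and cortical thickness are named as predictors in the Introduction but have no line on the form, so the regression cannot remove their effect.

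The cost is small. All five adjusters and density are already on the form, so no new measurement is needed. The density model has six factor coefficients, or 84/6 = 14 patients per coefficient. There is some loss of precision: 77.0% power for a partial r of 0.3 against 79.6% unadjusted, lower if density overlaps strongly with the adjusters and higher if they explain deviation. Restate the power for the adjusted analysis rather than enrol more patients.
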